Does the grant/contract involve a subcontract?

No

Study Location

Indicate if the research is/will be conducted at any of the following

NYSPI

This protocol describes research conducted by the PI at other facilities/locations

No

Lay Summary of Proposed Research

Lay Summary of Proposed Research

Separation Anxiety Disorder is a prevalent condition that has been newly placed in the Anxiety Disorders section of DSM5. Though separation anxiety was previously assumed to be confined to childhood, the National Comorbidity Survey Replication revealed a 6.6% lifetime and 1.9% 12 month prevalence of adult separation anxiety disorder (ASAD) in the community. Symptoms of ASAD include excessive distress when facing or anticipating separation from home or from attachment figures, as well as persistent worries about permanently losing or being abandoned by attachments, or of potential harm that may befall them during separations. Individuals with ASAD may be afraid to be alone or without an attachment figure close at hand, and may avoid leaving home, sleeping in bed alone, or sleeping away from home because of separation fears. **There have been no controlled trials or established medication or psychotherapy treatments for ASAD.**

treatments for ASAD. Vilazodone (Viibryd) appears to have an ideal pharmacological profile for efficacy for ASAD. In well-developed animal models of separation distress, 5HT1a agonists and serotonin reuptake inhibitors (SSRIs) have shown efficacy. In children, large randomized controlled trials have reported SSRI efficacy for mixed anxiety disorders which are highly comorbid in childhood, including separation anxiety disorder, social anxiety disorder, and generalized anxiety disorder.

In this randomized clinical trial, 40 adults with a principal diagnosis of ASAD, **no major depression of**

greater than mild severity, and no substance abuse disorders will be randomized to 12 weeks of treatment with vilazodone (flexibly dosed) or matched pill placebo. Outcome will be assessed in respect to symptomatic improvement, quality of life, adverse events and safety.

Background, Significance and Rationale

Background, Significance and Rationale

Separation Anxiety Disorder is a prevalent condition that has been newly placed in the Anxiety Disorders section of DSM5. Though separation anxiety was previously assumed to be confined to childhood, the National Comorbidity Survey Replication revealed a 6.6% lifetime and 1.9% 12 month prevalence of adult separation anxiety disorder (ASAD) in the community (NCS-R, Shear et al. 2006). Symptoms of ASAD include excessive distress when facing or anticipating separation from home or from attachment figures, as well as persistent worries about permanently losing or being abandoned by attachments, or of potential harm that may befall them during separations. Individuals with ASAD may be afraid to be alone or without an attachment figure close at hand, and may avoid leaving home, sleeping in bed alone, or sleeping away from home because of separation fears. There are no established medication or psychotherapy treatments for ASAD. Vilazodone (Viibryd) appears to have an ideal pharmacological profile for efficacy for ASAD. In well-developed animal models of separation distress, 5HT1a agonists and serotonin reuptake inhibitors (SSRIs) have shown efficacy (Winslow and Insel 1991; Simpson et al. 2007). In children, large RCTs have reported SSRI efficacy for mixed anxiety disorders which are highly comorbid in childhood, including separation anxiety disorder, social anxiety disorder, and generalized anxiety disorder (Walkup et al. 2001, 2008).

In this randomized clinical trial, 40 adults with a principal diagnosis of ASAD and no major depression or substance abuse disorders will be randomized to 12 weeks of treatment with vilazodone (flexibly dosed) or matched pill placebo. Outcome will be assessed in respect to symptomatic improvement, quality of life, adverse events and safety.

Specific Aims and Hypotheses

Specific Aims and Hypotheses

Aim 1. To assess the efficacy of vilazodone in the treatment of adult separation anxiety disorder (ASAD).

Primary Hypothesis (1): ASAD patients randomized to 12 weeks of vilazodone treatment will evidence greater symptomatic improvement than those randomized to placebo.

Hypothesis 2: ASAD patients randomized to 12 weeks of vilazodone treatment will evidence greater improvement in quality of life than those randomized to placebo.

Aim 2. To assess the safety and acceptability of vilazodone in the treatment of ASAD. Data will be collected on adverse events and duration of treatment.

Description of Subject Population

Sample #1

Specify subject population

adults with separation anxiety disorder

Number of completers required to accomplish study aims

40 randomized

Projected number of subjects who will be enrolled to obtain required number of completers

50

Age range of subject population

18-60

Gender, Racial and Ethnic Breakdown

We anticipate randomizing 30 women and 10 men; 20 Hispanics and 20 non-Hispanics; 27 whites, 10 African-Americans, and 3 Asians.

Description of subject population

Men and women, of any race and ethnicity, who present for treatment of DSM5 ASAD at the Anxiety Disorders Clinic of the New York State Psychiatric Institute.

Recruitment Procedures

Describe settings where recruitment will occur

Anxiety Disorders Clinic

How and by whom will subjects be approached and/or recruited?

Subjects who respond to treatment notices will be screened on the phone by a research assistant. After psychiatric assessment, the assessing psychiatrist will invite eligible subjects to participate in the study.

How will the study be advertised/publicized?

Patients will be obtained through: (a) word-of-mouth referrals from former patients, (b) referral from area medical and mental health professionals, (c) publicity about the study, including articles in local newspapers and magazines, appearances on local radio and television shows, etc., leading to self-referral of prospective patients, (d) recruitment notices placed in local media and on the internet (i.e. Facebook and Twitter), (e) Columbia Recruit Me, (f) Radio audio ads

Do you have ads/recruitment material requiring review at this time?

Yes

Does this study involve a clinical trial?

Yes

Please provide the NCT Registration Number

NCT01999920

Concurrent Research Studies

Will subjects in this study participate in or be recruited from other studies?

Yes

Describe concurrent research involvement

From the Anxiety Disorders Clinic psychiatric screening evaluation protocol (IRB #5029)

Inclusion/Exclusion Criteria

Name the subject group/sub sample

Adult Separation Anxiety Disorder patients

Create or insert table to describe the inclusion criteria and methods to ascertain them

Inclusion criteria:

Method of Ascertainment

1. Males or females between the ages of 18 and 60 History

2. Current primary (most clinically significant) diagnosis of DSM5 ASAD

SCID-I, Clinical Interview for ASAD

3. Able to give consent, fluent in English.

Clinical Interview

Create or insert table to describe the exclusion criteria and methods to ascertain them

1. Past or current DSM-IV diagnosis of any psychotic disorder; organic mental disorder or other cognitive disorder; bipolar disorder; or antisocial personality disorder. Current MDD of moderate or greater severity. Any other current primary Axis I disorder.

SCID-I, Hamilton Depression Scale
17-item total >18

2. Recent history (past 3 months) of substance or alcohol abuse or dependence (other than nicotine or caffeine).

SCID-I, urine toxicology

3. Suicidal ideation or behavior (in the past year) that poses a significant danger to the subject.

Psychiatric interview,
Score >2 on suicidal

ideation item of

Hamilton Depression

Scale

4. Medical illness that could significantly increase risk of vilazodone treatment or interfere with assessment of diagnosis or treatment response, including including organic brain impairment from stroke, CNS tumor, or demyelinating disease; renal, thyroid, hematologic or hepatic impairment; diabetes mellitus.

Medical chart review,
physical exam,
blood and urine tests
Consultation with
primary care doctor
when indicated.

5. Current or past history of seizure disorder (except febrile seizure in childhood

Medical history,
psychiatric

interview

6. History of non-response to ≥ 2 serotonergic reuptake inhibitor antidepressants (SSRIs and/or SNRIs) for the treatment of ASAD after adequate treatment trials (adequate treatment is defined as at least 8 weeks at an adequate dose[s] based on approved package insert recommendations).

7. Currently taking medication which has been effective for patient's ASAD.

8. For patients taking any ineffective psychoactive drug or herbal remedy, inability to tolerate or unwillingness to accept a drug-free period prior to beginning the study of 2 weeks or 5 half-lives (whichever is longer) before beginning study treatment, or ever having been treated with a depot antipsychotic. Fluoxetine washout period will be at least 5 weeks.

9. Requiring concomitant treatment with any prohibited medications, supplements, or herbal remedies, except for zolpidem, or zolpidem extended release for insomnia, which may be continued provided the medication has been used in a consistent manner for 4 weeks prior to randomization.

10. History of intolerance or hypersensitivity to vilazodone, SNRIs or SSRIs.

11. History of light therapy, electroconvulsive therapy, vagus nerve stimulation, transcranial magnetic stimulation, or any other experimental procedure for central nervous system disorders within 6 months of beginning this study.

12. Pregnancy, lactation; for women of childbearing potential, not using an effective birth control method (e.g. oral contraceptive or double barrier method) for the duration of the study.

13. Current formal psychotherapy initiated within 3 months of beginning this study. This includes: psychodynamic, cognitive-behavioral and interpersonal

Medical history

Psychiatric Interview

Psychiatric Interview

Psychiatric interview

Psychiatric Interview

Psychiatric Interview

History,
Physical exam,
blood pregnancy
test

History

therapies.

Waiver of Consent/Authorization

Indicate if you are requesting any of the following consent waivers

Waiver of consent for use of records that include protected health information (a HIPAA waiver of Authorization)

No

Waiver or alteration of consent

No

Waiver of documentation of consent

No

Waiver of parental consent

No

Consent Procedures

Is eligibility screening for this study conducted under a different IRB protocol?

Yes

Indicate NYSPI IRB #

5029

Describe Study Consent Procedures

The study psychiatrist will determine eligibility and fully explain study procedures. Patients interested in participating in research, who understand the risks and benefits of participation, will provide informed written consent to participate.

Patients currently taking psychotropic medication will be carefully evaluated for history of response.

Patients with inadequate response (persistent diagnosis of ASAD and meeting other inclusion/exclusion criteria) to current medication will be evaluated to ascertain that they are receiving the appropriate dose of that medication. They will be asked for consent to contact their prescribing doctor. After consultation with the pre-study prescribing doctor (if patient consented to contact), patients will be brought up to the maximal appropriate dose before determining their eligibility for this study. For patients who remain inadequately responsive after an adequate trial of their current medication, after the patient consents to participate in this study, the patient will be instructed on how to taper medication as clinically indicated to minimize discontinuation-related adverse effects. A study psychiatrist will see the patient weekly during this period **and complete a CGI-change scale -- a score of 6, much worse, or greater will trigger additional clinical assessment and prompt a discussion about continued participation.** Such subjects will discontinue prohibited medication for > 2 weeks, or 5 half-lives (whichever is longer), (and 5 weeks for fluoxetine), before proceeding with the pretreatment assessment. Patients with inadequate response to vilazodone will be excluded. Patients will not be withdrawn from effective treatment for the purpose of entering this study.

Indicate which of the following are employed as a part of screening or main study consent procedures

Consent Form

Persons designated to discuss and document consent

Select the names of persons designated to obtain consent/assent

[name]

[name]

Type in the name(s) not found in the above list

Study Procedures

Describe the procedures required for this study

Week 0 Baseline Visit. Randomization and Pretreatment Assessment Subjects will be randomized to vilazodone or placebo by a computer-generated random-number program, with treatment assignment sealed in opaque envelopes. Randomization sequences will be provided by the study statistician, who has no contact with study subjects.

Treatments. Subjects will initially receive 12 weeks of treatment with a single psychiatrist. The baseline treatment visit will last 45 minutes and subsequent visits 30 minutes. The first session will serve the following purposes: (1) confirm history; (2) obtain baseline ASAD symptoms; (3) provide explanatory framework for treatment; (4) address issues/concerns about medication; (5) describe specific side effects and characteristic medication response patterns; (6) establish a warm, empathic relationship, and engage the patient's trust; (7) explain the purpose and design of the study; and (8) make clear to the patient that the physician recognizes, understands and is familiar with ASAD. To ensure external validity, treating psychiatrists do not provide instructions about any exposure or cognitive therapy exercises. At the end of each visit pills will be provided as vilazodone 10 or 20 mg pills (depending on total dose), and matching placebo. A sufficient supply will be provided to last until the next visit (+/-3days), and unused medication will be collected from the patient at each visit. Brief ratings will be conducted by the psychiatrist to assess depression and adverse events, and vital signs will be assessed.

Dosage will initially be prescribed according to a fixed schedule, which may be modified in the case of nonresponse or intolerable side effects. It will start at 10mg/day and be increased to 20mg/day after 1 week and 40 mg/day after two weeks (optional). Patients without significant adverse effects who are not remitted (CGI-I=1) will have their dose increased to a maximum of 40 mg/day for the remainder of the study, if tolerated. Dosage can be held steady or lowered at any time during the study as clinically indicated in the event of adverse effects.

At the week visit 12 (or at premature termination), a complete medical workup (bloods, urine, EKG, physical exam) will be repeated. Participants at week 12 will be offered post-study open treatment and referrals, including the option of continuing on vilazodone if clinically appropriate. If discontinuation of study vilazodone is clinically indicated at any time, dosage will be tapered according to the following schedule, based on dose at endpoint:

Endpoint Dose Taper Schedule

40mg -->20mg for 4 days, 10mg for 7 days, then discontinue.

30mg	-->20mg for 4 days, 10 mg for 7 days, then discontinue
20mg	-->10 mg for 7 days, then discontinue.
10mg	--> discontinue

Subjects will also complete a computer-based Attention Bias Measurement at baseline, week 1, and week 12 visits, using procedures developed by Bar Haim (2010). This will assess bias to look toward angry or neutral faces, as a predictor and correlate of treatment response.

The stimuli are face photographs of 20 different individuals, with an angry and a neutral expression for each individual. The protocol consists of 120 trials (80 angry-neutral and 40 neutral-neutral presentations). Each trial begins with a fixation cross “+” presented in the center of the monitor for 500 ms. Immediately following termination of the fixation cue, the computer presents two faces of the same individual, positioned vertically. Each pair of faces displays one of two combinations of emotions (i.e., neutral and angry, or neutral and neutral).

After presentation of the face pair for 500 ms, a probe (“<” or “>”) appears in the location of one of the faces. Participants are instructed to press the button (left or right, corresponding to the direction of the probe pointer).

The task takes 5-10 minutes to complete.

You can upload charts or diagrams if any

Criteria for Early Discontinuation

Criteria for Early Discontinuation

Adherence and termination of study treatments

Adherence -- Rules of the treatment protocol will be carefully explained to patients by intake screeners and in consent forms. Patients who miss study visits will be actively followed up by phone and mail. Serious protocol violations, such as use of proscribed outside treatments or substance abuse, will be reviewed by the PI and will result in withdrawal from the study treatment. Substance use will be assessed by initial drug screen and subsequent patient report. If clinical suspicion of substance use arises based on erratic behavior, alcohol on breath, and other signs and symptoms, spot toxicology screens will be used. Treating psychiatrists will monitor patient drinking behavior with repeated queries over the course of treatment. If patients are withdrawn from the study treatments, staff will make every effort to make this event constructive and empathic. Patients will continue to be assessed for the full **12** weeks of the study. A pill count will be conducted after each visit to assess adherence to medication schedule.

Criteria for removal from study treatment, including non-adherence. These will be defined as follows: a) patients who deteriorate in treatment, as defined during weeks 0-12 by CGI-I score > 5 and remain similarly impaired at re-assessment one week later; b) patients who commit serious violations of the protocol; and c)

patients who miss more than 3 consecutive days of medication or a total of 12 days within weeks 0-12. Patients who are non-adherent with a clinic visit will be contacted by the investigator to elucidate reasons for non-adherence.

Blood and other Biological Samples

Please create or insert a table describing the proposed collection of blood or other biological specimens

Prior to study entry, and at the week 12 visit, **25ml** of blood will be drawn for: **oxytocin levels**, CBC, chemistry, thyroid tests, and in women, pregnancy test. Urine will be obtained for drug screen and urinalysis.

Assessment Instruments

Create a table or give a brief description of the instruments that will be used for assessment

(1 hour) Structured Clinical Interview for DSM IV (SCID-I) (First et al., 2002), used to determine Axis I disorders

(10 min) Structured Clinical Interview for Separation Anxiety Disorder (Cyranowski et al., 2002), modified for DSM-5. The eight separation anxiety disorder criteria are rated for both childhood (rated at baseline only) and past week time frames, scored as 0 (not at all), 1 (sometimes), 2 (often) or ? (don't recall). In keeping with the DSM-5 guidelines, endorsement of three or more of the eight criterion symptoms (symptoms rated as '2' or 'often') is used as a threshold to determine categorical (yes/no) diagnosis of separation anxiety disorder. Scores on each of the eight items are also summed to produce a continuous measure of separation anxiety symptoms experienced during childhood and adulthood (range for each scale=0–16).

(10 min) Hamilton Rating Scale for Depression (Hamilton, 1960) This standard scale will be used to assess severity of depression.

(10 min) Quality of Life Enjoyment & Satisfaction Questionnaire (Q-LES-Q, Endicott et al, 1993): self-rated assessment of quality of life.

(5 min) Arizona Sexual Experiences Scale (ASEX) (McGahuey et al., 2000): will be used to assess sexual functioning as a self-rating. It is a five-time rating scale and has been shown to have adequate internal consistency, test-retest reliability, and convergent and discriminant validity.

(5 min) Anxiety Sensitivity Index (Peterson and Reiss 1993): self-rated and measures anxiety sensitivity or fear of anxiety-related sensations

(1 min) Sheehan Disability Scale (Sheehan 1983): self-rated and assesses functional impairment in work/school, social life, and family life.

(10 min) Hamilton Anxiety Scale (Hamilton 1959): measures the severity of both psychic and somatic anxiety.

(5 min) Clinical Global Impression-Improvement Scale (CGI-I), a quickly administered and widely used observer rating, will evaluate overall clinical status on a 1-7 point likert scale (Guy, 1976).

(5 min) Side Effect Checklist (SECL) A checklist of 27 symptoms commonly occurring as side effects to SSRIs will be rated on a 4-point anchored scale from 0-none to 3-severe.

(15 min) Adult Separation Anxiety – 27 Scale (Manicavasagar et al, 2003) 27 items pertaining to adult separation anxiety, each self-rated on a four-point scale.

(15 min) Attachment Style Questionnaire (Feeney et al., 1994) 40 items relating to quality of adult relationships, each self-rated on a four-point scale.

Please attach copies, unless standard instruments are used

Off label and investigational use of drugs/devices

Choose from the following that will be applicable to your study

Drug

Select the number of drugs used in this study

1

Drug #1

Name of the drug

Vilazodone

Manufacturer and other information

Forest Laboratories

Vilazodone is an SSRI and 5HT1a receptor agonist, FDA-approved for depression.

Approval Status

No IND is required

Choose one of the following options

FDA has determined that IND is not required

Research Related Delay to Treatment

Will research procedures result in a delay to treatment?

Yes

Maximum duration of delay to any treatment

Maximum duration of delay to any treatment would be one week for assessments, except that patients who are to be tapered off ineffective medication will have an additional delay of 2-4 weeks for washout, plus the time needed to taper off.

Patients randomized to placebo could have active treatment delayed by another 12 weeks (maximum total of 17 weeks including assessment and washout, if needed).

Maximum duration of delay to standard care or treatment of known efficacy

The is no treatment of known efficacy for ASAD, as there have been no reported clinical trials of medication or psychotherapy for this condition. However, based on studies of separation anxiety disorder in children, standard care might consist of cognitive-behavioral therapy or SSRI medication. The maximum duration of delay to standard care would be 17 weeks, as described above for subjects who needed a 5-week washout, and were then randomized to placebo.

Treatment to be provided at the end of the study

Three months of open medication treatment, including one month of free medication.

Clinical Treatment Alternatives

Clinical treatment alternatives

Based on studies of childhood separation anxiety disorder, the main treatment alternatives are cognitive-behavioral therapy or SSRI medication.

Risks/Discomforts/Inconveniences

Risks that could be encountered during the study period

a. Risks Associated with Treatment Procedures:

Medication Treatment: The most commonly reported side effects associated with therapeutic doses of vilazodone (incidence $\geq 5\%$ and at least twice the rate of placebo) are: diarrhea, nausea, vomiting, and insomnia. Uncommon potential side effects include serotonin syndrome, increased bleeding, mania and low blood sodium. Suicidal ideation has been reported to sometimes be associated with antidepressant treatment. Vilazodone may have negative interactions with other medications a patient may take over the course of the study.

Medication Discontinuation: Tapering of vilazodone that is too abrupt may lead to symptoms such as dizziness, sensory disturbances, agitation or anxiety, nausea and sweating. For patients who are tapered off study medication by study psychiatrists for any reason, tapering will be gradual and closely monitored.

Prohibited Treatments: An additional risk is that participants will not be able to benefit from all available treatments, as they will be prohibited from receiving other potentially helpful treatments during the study, including other psychotropic medications or initiating psychotherapy.

Placebo: Patients have a 50% chance of being assigned to placebo for the 12 weeks. These participants will not be receiving active pharmacological treatment, and their condition could fail to improve or could worsen during this period.

Blind Treatment: Another risk is that participants will not be told whether they were assigned to vilazodone or placebo until completing the 14 week assessment period, except in the event of a medical emergency. This may delay or interfere with selection of optimal post-study treatments.

b. Risks Associated with Assessment Procedures:

Venipuncture: Mild discomfort and, rarely, a small arm bruise, clot or infection may occur at the site of the blood drawing.

Self-Report Measures, Assessor Ratings: Patients could develop mild to moderate emotional discomfort or frustration associated with psychiatric interviewing or filling out questionnaires.

Describe procedures for minimizing risks

To minimize treatment risks, patients will be screened for conditions that significantly increase risks of treatment, adverse effects and vital signs will be monitored at every visit, and dosing is flexible to allow reductions in the event of adverse effects. Patients will be educated about potential adverse interactions with other medications they may wish to take and advised to contact study physicians before starting new medications. Patients will be informed that they may withdraw from study treatment at any time.

Randomization codes will be broken for patients upon their termination from the study, or earlier in the event of a medical emergency.

Venipuncture will be conducted with standard safety procedures.

Self-Report Measures, Assessor Ratings: Study clinicians are skilled at dealing with distress and will make efforts to help clients to feel as comfortable as possible (e.g., by giving breaks during an evaluation, offering encouragement).

Methods to Protect Confidentiality

Describe methods to protect confidentiality

All data with identifying information will be stored in locked file cabinets or password-protected computer files. Data being analyzed will be identified by subject codes and identifying information will be removed. The identity of patients will not be revealed in the presentation or publication of any results from the project. All assistants and others working on the project will be educated about the importance of strictly respecting patients' rights to confidentiality.

Will the study be conducted under a certificate of confidentiality?

No

Direct Benefits to Subjects

Direct Benefits to Subjects

The potential direct benefit to patients who enter this study will be to obtain relief from ASAD symptoms to improve their quality of life. Vilazodone is an SSRI, and SSRIs have appeared efficacious for childhood separation anxiety disorder. Also, Vilazodone is FDA-approved for the treatment of depression, and it may be helpful for comorbid symptoms of depression in ASAD.

Compensation and/or Reimbursement

Will compensation or reimbursement for expenses be offered to subjects?

Yes

Please describe and indicate total amount and schedule of payment(s).

Include justification for compensation amounts and indicate if there are bonus payments.

Participants will receive \$30/evaluation for completing each visit 2,3,4,5,6, and 7; \$60/evaluation for completing each visit 1 and 8, to be paid by cash after each visit (maximum total of \$300 over the 12 weeks of the study).

Subjects will be paid for each of these assessments that are completed at the specified week, regardless of whether they are continuing on study treatment or not.

Uploads

Upload the entire grant application(s)

Upload copy(ies) of unbolted Consent Form(s)

CF unbolted 9.30.16.pdf

Upload copy(ies) of bolded Consent Form(s)

CF bolded 9.30.16.pdf

Upload copy(ies) of recruitment materials/ads to be reviewed

ads sep anxiety revision 1.pdf

ASAD ad 9.6.16.pdf

Sep_Anx_Ad_pull_tabs.pdf

Sep_Anx_Ad_loved_one.pdf

Vilaz_Paid_Craigslist_Posting_.pdf

Sep Anx Ad partner or spouse (no stamp).pdf

Sep Anx Ad child (no stamp).pdf

Upload copy(ies) of the HIPAA form

HIPAA_09.06.16.pdf

Upload any additional documents that may be related to this study

Continuation_memo.approved_pending.09.30.16.pdf

References

References

Bar-Haim Y. Research review: Attention bias modification (ABM): a novel treatment for anxiety disorders. J Child Psychol Psychiatry. 2010 Aug;51(8):859-70.

Cyranowski JM, Shear MK, Rucci P, Fagiolini A, Frank E, Grochocinski VJ, et al. Adult separation anxiety: psychometric properties of a new structured clinical interview. Journal of psychiatric research.36:77-86.

2002 Gabbard G. (ed.) Gabbard's Treatments of Psychiatric Disorders, 5th Edition. American Psychiatric Publishing Inc, Washington, DC, In Press

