Data Analysis Plan for IRB #6856: Vilazodone in Separation Anxiety Disorder

Aggregate statistics for demographic and clinical characteristics of the two groups were calculated and compared using chi-square tests and t-tests, as appropriate. All quantitative post-randomization outcomes were graphed and their distribution assessed for outlier values. To compare outcomes in the two groups, mixed effect logistic regression was used for the categorical outcomes and mixed effect regression models for quantitative outcomes, with subject-specific random effects and a first order auto-correlation structure for observations within the same individual. Time was included in the model as an additive factor (due to relatively low sample size, we did not test for differential time effect through interaction with group).

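### The primary hypothesis names a symptom domain but no deciding measure, significance level or multiplicity rule, and the SAP leaves the role of baseline unstated

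*Protocol*

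**What the plan says.** **Hypotheses (protocol, Specific Aims and Hypotheses).** The Primary Hypothesis is that "ASAD patients randomized to 12 weeks of vilazodone treatment will evidence greater symptomatic improvement than those randomized to placebo". Quality of life comes second: "Hypothesis 2: ASAD patients randomized to 12 weeks of vilazodone treatment will evidence greater improvement in quality of life". Symptoms therefore rank above quality of life, and the gap lies inside the symptom domain.

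**Measures (protocol, Assessment Instruments).** Two scores address separation anxiety directly.
- The structured interview: "Scores on each of the eight items are also summed to produce a continuous measure of separation anxiety symptoms", range 0-16. The adult items use a past-week time frame; the childhood items are rated at baseline only.
- The self-report scale: "27 items pertaining to adult separation anxiety, each self-rated on a four-point scale".

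The same section also lists the interview's yes/no diagnosis, the Hamilton Anxiety Scale and the CGI-I, which "will evaluate overall clinical status on a 1-7 point likert scale". Elsewhere the protocol uses the CGI-I for dose adjustment (Study Procedures) and for removal from study treatment (Criteria for Early Discontinuation). No measure is called primary.

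**Analysis (SAP, a single paragraph).** It reports that "mixed effect logistic regression was used for the categorical outcomes and mixed effect regression models for quantitative outcomes", with subject-specific random effects and first-order autocorrelation. "Time was included in the model as an additive factor", and a group-by-time interaction was not tested. It states no deciding outcome, significance level, multiplicity rule or baseline term. The nearest reference to baseline is "All quantitative post-randomization outcomes were graphed", which describes the graphs and not the model. The text is undated and in the past tense.

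**The concern.** Aim 1 is an efficacy aim, and the Lay Summary says that there have been no controlled trials in this condition. A reader will have no earlier trial against which to check a chance finding, so the error rate of this one needs to be defined.

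With two scores that each fit the hypothesis and no rule for choosing between them, the plan does not define one test. If the choice is made after the results are seen, the nominal error rate no longer applies.

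The baseline question is separate. With no group-by-time term, the SAP's model yields one group effect per outcome, averaged over the visits in the model. Whether baseline is one of those visits changes what the effect estimates. Whether baseline is used as a covariate changes how precisely it is estimated.

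**Working it through.** The documents give no significance level, power, effect size or standard deviation, so there is no planned figure to reproduce. What follows illustrates size only.

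**Inputs from the documents.** 40 randomized (Description of Subject Population) and a 50% chance of placebo (Risks/Discomforts/Inconveniences), hence about 20 per arm. Two separation-anxiety scores (Assessment Instruments).

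**Assumed.** Two-sided 0.05 per test; a significant result on either score counts; no true effect; correlation r between the two scores of 0.5 to 0.9.

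**1. Two scores, either one sufficient**

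Falsely favouring vilazodone: P(either) = 0.025 + 0.025 - P(both). With bivariate normal test statistics:

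| r | P(both) | P(either) |
|---|---|---|
| 0.5 | 0.0046 | 0.0454 |
| 0.7 | 0.0083 | 0.0417 |
| 0.9 | 0.0148 | 0.0352 |

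Any false positive, in either direction, on the same approximation: 0.091, 0.083 and 0.070.

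Simulating t-tests on 38 degrees of freedom (200,000 null trials per setting) gives 4.6%, 4.2% and 3.5% favouring vilazodone, and 9.2%, 8.5% and 7.2% in either direction.

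A repeated-measures check used one group effect over seven post-baseline visits. Seven is assumed from the eight paid visits in the Compensation section; no passage says that either scale is given at each. With a random-intercept share of 0.5 and autocorrelation of 0.5, both assumed, the results were 4.5%, 4.3% and 3.6%, and 9.0%, 8.3% and 7.1%. The simple calculation therefore carries over to a model of the SAP's kind.

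**2. Baseline as a response row**

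Treatment cannot affect the baseline visit. Suppose the true effect is constant after baseline and there are K visits including baseline. With equal visit weights, the additive group term keeps (K-1)/K of the effect:
- K = 4: 3/4 = 75%
- K = 8: 7/8 = 87.5%

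Under the SAP's autocorrelation structure with equally spaced visits and complete data, the first and last visits carry more weight. The baseline weight is 1/[2 + (K-2)(1-ρ)], and a random intercept does not change it. With ρ = 0.5 assumed:
- K = 4: 1/(2 + 1) = 0.333, so 67% is kept
- K = 8: 1/(2 + 3) = 0.20, so 80% is kept

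**3. Baseline left out altogether**

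Take one endpoint visit, 20 per arm and an assumed true difference of 0.8 SD. Power = Φ(0.8 × √(20/2) / √v - 1.96), where v = 1 if baseline is ignored and v = 1 - c² if it is a covariate, with c the baseline-endpoint correlation.
- Ignored: Φ(2.530 - 1.96) = 72%
- c = 0.3, v = 0.91: 76%
- c = 0.5, v = 0.75: 83%
- c = 0.7, v = 0.51: 94%

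**The case against.** **The designation may exist elsewhere.** The protocol gives a trial registration number, and the registry record was not available here. A primary measure may have been fixed there before any data were seen. This stands, and it limits the severity. It does not remove the gap in the SAP, which still has to identify the test.

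**The directional inflation is modest.** Hypothesis 1 is that the drug is better, so the relevant error is a false result in its favour. With two scores that rate stays below 5%. This is fair, and the directional figure should lead. Even so, 4.6% is nearly twice 2.5%.

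**A reader might count the CGI-I, the Hamilton Anxiety Scale or the yes/no diagnosis and infer a much larger error rate.** More candidate measures would raise the rate. But the SAP sends categorical outcomes to logistic regression and does not say how the CGI-I is classed. A calculation for normally distributed outcomes need not apply to it, so no figure is given.

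**A reader might infer that the open baseline choice inflates the error rate in the same way.** That would require two competing models to be fitted and the better one reported. The SAP describes one model per data type, and in simulation each baseline reading alone held close to 5% (0.047 to 0.052). The supported criticism is dilution or lost precision.

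**A reader might infer that the measure was in fact picked after the data were seen.** The past tense does not show that. The documents leave room for selection; they do not show that it occurred.

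**Conclusion.** The point holds in a limited form. The hypotheses are ranked between domains, but within the primary domain neither document says which score decides, at what level, or what follows if the scores disagree. For the two separation-anxiety scores, the chance of a false claim for vilazodone rises from 2.5% to about 3.5-4.6%, and of any false positive from 5% to about 7-9%. These figures rest on the assumed 0.05 level, the either-score rule and correlations of 0.5 to 0.9, none of which is in the documents.

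The baseline omission is a separate matter of estimation. If baseline is a response row, the group effect is diluted, to about 67-88% of its post-baseline value in the cases worked above. If baseline is left out, precision is lost.

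This should be fixed. It would be too strong to say that the trial's error rate is uncontrolled, because an earlier designation in the registry record can be neither confirmed nor excluded.

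**What to change.** 1. **Deciding measure.** If one symptom measure was designated primary before outcome data were seen, name it in the SAP as the sole test of Hypothesis 1, using the group effect at two-sided 0.05, and cite the dated source. If there was no such designation, report every symptom measure as an estimate with its interval and label the efficacy result exploratory. A primary named now, without a dated source, would not restore the 5% rate.
2. **Baseline.** For the separation-anxiety scores, fit the post-randomization visits as responses with the baseline score as a covariate, and say so in the SAP. The additive-time model can otherwise stay as it is.
3. **Other symptom scales.** Make them secondary, with no separate efficacy claim.

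**Cost.** If a dated choice exists: a few sentences, a citation, and one refit if baseline was handled differently. If none exists: the efficacy claim becomes exploratory. In either case, significance on another scale alone no longer supports the primary hypothesis.
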